To ensure quality results, we will conduct formal training and recertification on all field procedures. The HVA will be required to take a NIOSH-approved spirometry course, which is a well-recognized training among medical professionals. In addition, all HVAs will complete the online exam and submit 10 practice tests administered by a certified spirometry expert. All spirometers will undergo standard quality checks before use in the field. To ensure high quality control and HVA feedback, we will use reviewing software similar to the one recently developed specifically for the EasyOn spirometer by Hankinson Consulting, Inc. (Athens, GA). An expert in pulmonary function quality control will review all tracings on a weekly basis and override any software-provided readings if needed. The quality scores and other results will be electronically forwarded to field coordinators who will feed the quality information to the HVAs. If an unexpected number of unacceptable tracings occur, the HVA in question will be retrained.

Participants who answer yes to any of the following questions will not undergo spirometry during the visit:

- In the past three months, have you had any surgery to your chest or abdomen?
- In the past three months, have you had a heart attack or stroke?
- In the past three months, have you had a detached retina or have you had eye surgery?
- In the past three months, have you been hospitalized for any other heart problem?
- Are you pregnant?
- Are you currently taking medication for tuberculosis?

Our exclusion questions include those used in BOLD [Buist, et al. 2007] and PLATINO [Menezes, et al. 2005], multinational studies that enrolled over 14,000 adults over age 40 years for pre and post bronchodilator spirometry with only trained technicians. No adverse events occurred in either the BOLD or PLATINO studies. These exclusions are considered very conservative and these questions are not generally asked before spirometry is done in clinical practice. Note that exclusions for having a resting heart rate > 120 bpm is included.

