If the participant asks that evaluation results be sent to their health care provider, the HVA will collect the name and contact information for the health care provider and record the information in the CAPI system. Within a month of the visit, the results of evaluations and advice regarding health care referrals will be shared with the participant's health care provider, if any abnormal evaluation findings were detected. Any evaluation finding that does not fall within the normal ranges will result in a letter to the health care provider. The health care provider will receive a cover letter that briefly describes the study and the reason the results are being sent, as well as a copy of the summary report that all participants will receive by mail. If the participant does not have a health care provider, the HVA will provide information about local health care resources, if warranted, based on abnormal evaluation findings. Participants who receive a referral will be instructed to present the health care provider with the results handouts at the time of the referral visit.

The advice that participants receive about medical referrals will be based on level of urgency of their findings. For example, the referral levels for hypertension are based upon recently published guidelines from the American Heart Association (AHA) for blood pressure. We tended to select the more conservative guidelines when there were several choices, given the fact that the community under study includes many without access to care and the fact that our study will be highly visible and we want to err on the side of caution. Nonetheless, levels of urgency can vary across practitioners and communities; setting levels too low may unnecessarily over-burden area medical care systems, while setting them too high may put participants at risk. The frequency of referral for care will be monitored as will the outcomes for referrals deemed urgent. If it is determined that we are making too many unnecessary referrals or that these guidelines are inconsistent with local practice, we will consider other less conservative standards. Any proposed changes would be brought back to the IRB for evaluation. Participant referrals or follow-up instructions will be categorized into one of the five classifications below, based upon their test results or findings (see Table 2 below).

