1. **Emergency:** The HVA is instructed to immediately offer to assist the participant or family members in contacting emergency medical services or their treating physician. If the participant declines this immediate assistance, the HVA will continue with the minimal risk components of the visit, omitting the blood collection and spirometry components at that time. If it is later determined that the emergency situation has resolved, we will attempt to perform these remaining components after confirming at that time that the emergency situation is indeed resolved.

2. **Urgent:** The Urgent referral category is divided into two levels depending upon the urgency of the results or findings.

Level 1: the participant is asked to follow-up with their health care provider in 72 hours.

Level 2: the participant is asked follow-up with their health care provider in one week or two week intervals depending on the urgency of the results. HVA or Call Center staff will follow-up with all "Urgent" referral category participants by phone to assess their disposition.

3. **Check-Up:** The participant is asked to follow-up with their health care provider within one to two months.
4. **Routine Care:** The participant is advised to seek guidance from health care providers to learn about healthy lifestyle choices to help prevent disease.
5. **No Referral:** Results are within the normal range.

Alert Levels for Laboratory Results & Spirometry Interpretations:

CBC Abnormalities:

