Alert levels for abnormalities associated with the CBC components that are reported to the participant (i.e., white blood cell count, hemoglobin concentration, hematocrit percentage or platelet count) will trigger “Urgent” referrals. Within one week of Alert Level findings being reported by the laboratory, participants will be notified by phone and advised to follow-up with a health care provider in either 72 hours for Alert Level 1 findings or one-to-two weeks for Alert Level 2 findings (as indicated in Table 2). The chosen laboratory urgent referral action levels were based upon values used for the Jackson Heart Study of African-American males and females ages 35-84 living in the Jackson, Mississippi area and reference values used by our central diagnostic laboratory. The Alert Level 1 referrals for total white blood cell count ($\leq 1.1 \times 10^3 / \mu\text{L}$), hemoglobin ($\leq 6.1 \text{ g/dL}$) and hematocrit ($\leq 18.1\%$) lead to a recommendation for participant follow-up in 72 hours. These thresholds are based upon the “panic levels” from our central diagnostic laboratory.

Spirometry Abnormalities:

Alert Level for post-exam spirometry interpretations will be reported to participants by phone within one week of receipt from the central laboratory. Participants will be advised to follow-up with a health care provider within one week (as indicated in Table 2). The spirometry alert level for an urgent referral utilizes the lower limits of normal (LLN) which is an index derived from population data based on race, age, sex, and height. The LLN is designed to be the 5th percentile for the index (FEV1, FVC, & Fev1/FVC) of interest (Roberts 2006). The use of FEV1 < 50% results in a “severe classification” regardless of obstructive or restrictive conditions and is consistent with ATS guidelines, assuming a valid and interpretable test (Pellegrino 2005). Given the nature of worker cohorts we do not expect to see very many participants in the severe category.

Table 2. Medical Care Referral Guidelines

Evaluation	Findings	Referral	Comments
Blood Pressure	SBP ≥ 180 or DBP ≥ 110	Urgent*. Seek care as soon as possible if confirmed as a chronic condition. *Based on AHA 2010 guidelines	HVA to offer to contact 911 or help assist with referral as indicated. HVA / Call Center to follow up with participant by phone ASAP.

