Pulmonary function testing is considered safe. The primary risk, which is exceedingly rare, is fainting in older participants with impaired lung function. We minimize the chance that this rare event will occur first through our very conservative exclusions for pulmonary function testing – any heart attack or hospitalization for other heart problem or stroke in the past 3 months. Pregnant women will not undergo pulmonary function testing until at least 3 months post-partum. To further minimize risk of fainting, pulmonary function testing is done in a seated position, and study staff will be trained to look for signs of dizziness or other problems and to stop the maneuver if necessary. The risk of infection is all but eliminated by using disposable mouthpieces (spirettes). These disposable mouthpieces have the additional protection of having a built-in bacterial filter. In the PLATINO [Menezes, et al. 2005] and BOLD [Buist, et al. 2007] studies, home

visits were conducted on 14,000 adults over age 40 by trained technicians only, without physicians present, and no adverse events were associated with in-home spirometry.

There may be some minor discomfort associated with blood collection, including temporary pain, bruising, or swelling at the phlebotomy site. Fainting during blood collection is exceedingly rare.

There is also a remote risk of accidental disclosure of study information. Measures that will be taken to guard against accidental disclosures include maintaining complete confidentiality of the questionnaires and laboratory samples, use of secure data systems, and staff training (see Section 10.3 – Participant Confidentiality). Participants will also be warned of the possibility of loss of privacy should their de-identified data distributed through controlled access procedures be linked back to them in ways that cannot be foreseen at present.

4 Adverse Event Reporting

Adverse events associated with this study procedures are expected to occur very infrequently. Most of the potential risks associated with study procedures (see Section 3.2) is limited to mild, transient discomforts of no clinical significance. Only clinically significant adverse events will be reported to the IRB. Examples of clinically significant adverse events include:

- fainting during spirometry or blood collection
- respiratory distress induced by spirometry that requires medical attention

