6.6.7 Long Distance Corridor Walk (LDCW)

Insufficient cardiovascular fitness may be a major mechanism through which different behaviors and diseases contribute to functional decline; a key landmark on the pathway from independence to disability. As substantial decline in exercise tolerance may precede recognition of mobility-related difficulty, particularly in

sedentary individuals, low exercise tolerance may be an early indicator of impending functional limitation.

The LDCW, a walking-based test of exercise tolerance and fitness level, developed for use in the Health ABC study, was designed to minimize shortcomings associated with self-paced walking tests. [46] The participant is asked to walk four hundred meters at their normal pace and the time to accomplish this task is recorded. Four hundred meters is the approximate distance an average healthy older adult can cover in 6 minutes and is comparable to the reference distance (1/4 mile) of a commonly used self-report measure of mobility-related difficulty. [46] Participants are told that they will be timed but are advised to walk as quickly as they can, without running, at a pace they can maintain over the 400 meters. The LDCW will not be performed with participants whose systolic blood pressure is greater than or equal to 180, diastolic blood pressure greater than or equal to 110, heart rate less than or equal to 40 beats per minute, or heart rate greater than or equal to 120 beats per minute. Participants who report recent (within last three months) heart attack or myocardial infarction, angioplasty or stent placement, unstable angina or heart surgery will also be excluded from the LDCW. Further, participants are excluded if they are not comfortable walking long distances without assistive devices or if they are wearing shoes that make walking difficult.

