6.9 Pulmonary Function Testing (PFT)

Pre and post-bronchodilator pulmonary function testing (PFT) will be conducted according to ATS/ERS guidelines [48]. Bronchodilation will be achieved through the administration of 4 metered doses of albuterol (90 µg per actuation, 4 puffs) through a spacer, with 30 seconds between puffs. Post-bronchodilator spirometry will take place 10-15 minutes after bronchodilator administration.

PFT will be performed using a portable, ultrasound transit-time based spirometer (EasyOn; NDD Medical Technologies, Chelmsford MA, USA, or a comparable model). A full Forced Vital Capacity maneuver will be conducted. We will obtain three ATS acceptable forced expiratory maneuvers out of a maximum of eight attempts before and after bronchodilator administration. Spirometry will be conducted with the participant seated and wearing a disposable nose clip. We will use new individually packaged, disposable mouthpieces for each subject and a new spacer for each subject. All spirometers will undergo standard quality control checks each day they are used.

To the extent possible, we will ask participants to not use their asthma inhalers on the day of the examination. We will record the timing and dosage of all asthma medications over the preceding seven days.

Participants who answer yes to any of the following questions will not undergo spirometry during the visit:

- In the past three months, have you had any surgery to your chest or abdomen?
- In the past three months, have you had a heart attack or stroke?
- In the past three months, have you had a detached retina or have you had eye surgery?
- In the past three months, have you been hospitalized for any other heart problem?
- Are you pregnant?
- Are you currently taking medication for tuberculosis?

In addition, participants with a blood pressure > 180 mmHg systolic or > 110 mmHg diastolic, or with a heart rate > 120 or < 40 beats per minute will not be tested.

Our exclusion questions include those used in BOLD [49] and PLATINO [50], multinational studies that enrolled over 14,000 adults over age 40 years for pre and post bronchodilator spirometry with only trained technicians. No adverse events occurred in either the BOLD or PLATINO studies. These exclusions are considered very conservative and these questions are not generally asked before spirometry is done in clinical practice.

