6.13 Reports to Participants and Health Care Referrals

During each clinical exam visit, clinical staff will measure height and weight to calculate BMI, blood pressure, spirometry, and hemoglobin A1c and lipid levels. The participant will receive a form with the results of these tests/measurements, standardized clinical interpretations, and advice for seeking care. In addition to providing the participant form and recommended actions (see Table 4), participants who do not have a primary care provider or who cannot afford to pay for care will be referred to a local clinic that provides care for services based on a sliding scale.

Table 4. Recommendations for Action based on Medical Findings

Evaluation	Findings	Recommended Actions
Blood Pressure	SBP \geq 180 or DBP \geq 110	Seek care as soon as possible as this is a potential emergency health condition. Emergency Care Needed. A hypertensive crisis exists when blood pressure reaches levels of 180 or higher for the systolic (top) number OR 110 or higher for the diastolic (bottom) number. There is no safe duration for blood pressure to remain in this range.
	SBP 160 to 179 or DBP 100 to 109	See a health care provider within the next month to have your blood pressure rechecked and managed.
	SBP 140 to 159 or DBP 90 to 99	See a health care provider within the next two months to have your blood pressure rechecked and managed.
	SBP 120 to 139 or DBP 80 to 89	Find out from a health care provider if any additional evaluations or lifestyle changes are indicated.
	SBP < 120 AND DPB < 80	No recommendation.
Resting Heart Rate	HR > 120 bpm	You should see a health care provider as soon as possible . A very high heart rate can be a sign of a heart problem or other medical conditions.
	101 \leq HR \leq 120 bpm	A high heart rate may be due to a medical problem or other causes. You should see a health care provider within the next month .
	40 \leq HR \leq 59 bpm	A low heart rate may be normal for some individuals. In others, it may be due to a medical problem. You may want to share this report with your health care provider at your next visit.
	HR < 40 bpm	You should see a health care provider as soon as possible . A very low heart can be a sign of a heart problem or other medical conditions.
	60 \leq HR \leq 100	No recommendation.
BMI	Obese (\geq 30)	People who are obese are at higher risk for chronic conditions such as high blood pressure, diabetes, and high cholesterol.

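### Home spirometry has no blood-pressure stop, and Table 2 labels SBP ≥180 or DBP ≥110 Urgent, so the Emergency rule that omits spirometry is not attached to that reading

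*Protocol*

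**What the plan says.** Home visit:

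- Section 2.10.4.1 states that "Participant referrals or follow-up instructions will be categorized into one of the five classifications below, based upon their test results or findings", and refers to Table 2. The classes are Emergency, Urgent, Check-Up, Routine Care and No Referral.
- In the Emergency class the agent offers immediate help. If it is declined, the agent continues with the minimal-risk parts of the visit, "omitting the blood collection and spirometry components at that time". The omitted parts may be done later, once the situation has resolved. The Urgent class means care within 72 hours, or within one or two weeks, and omits nothing.
- The top blood-pressure row of Table 2 (SBP ≥180 or DBP ≥110) is labelled Urgent. Its advice is "Seek care as soon as possible if confirmed as a chronic condition"; its comment tells the agent to offer a 911 call or help with referral.
- Section 2.9.4.2 lists six screening questions that rule out spirometry and ends: "Note that exclusions for having a resting heart rate > 120 bpm is included". Section 3.2 summarises the exclusions as "any heart attack or hospitalization for other heart problem or stroke in the past 3 months", with pregnancy added.

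Clinic examination (Addendum 3):

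- Section 6.13, Table 4, at SBP ≥180 or DBP ≥110: "Seek care as soon as possible as this is a potential emergency health condition".
- Section 6.9 withholds spirometry from "participants with a blood pressure > 180 mmHg systolic or > 110 mmHg diastolic".
- Section 6.6.7 withholds the 400 m walk from participants "whose systolic blood pressure is greater than or equal to 180, diastolic blood pressure greater than or equal to 110".

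**The concern.** The instruction to leave out spirometry depends on a class label, and the reading that most plainly calls for it carries a different label. The exclusion list in 2.9.4.2 would be the second line of defence, but it does not mention blood pressure. A home participant with a crisis-level reading who declines the 911 offer can therefore go on to forced spirometry without any sentence in the protocol body being broken. The clinic would withhold the test from the same person. What is at stake is participant safety and consistency between two parts of one protocol; no estimate, power figure or sample size is affected.

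**Working it through.** No arithmetic applies. The check sets the rules side by side for the same readings.

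| Rule | Home visit | Clinic (Addendum 3) |
|---|---|---|
| Class or advice at SBP ≥180 or DBP ≥110 | Urgent, with a 911 offer (Table 2) | Emergency care (Table 4) |
| Spirometry stop on blood pressure | None (2.9.4.2, 3.2) | >180 or >110 (6.9) |
| Spirometry stop on heart rate | >120 bpm (2.9.4.2) | >120 or <40 bpm (6.9) |
| 400 m walk stop on blood pressure | Not done | ≥180 or ≥110 (6.6.7) |

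**Step 1: a home participant at 190/115 who declines help.** Table 2 gives Urgent. The Urgent class omits nothing. None of the six questions concerns current blood pressure, and heart rate may be normal. Result: spirometry is not excluded. In the clinic, 190 > 180 and 115 > 110, so spirometry is withheld.

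**Step 2: does other home-visit text close the gap?** Section 2.10.1 names hypertensive crisis among findings to be handled at once and refers to 2.10.6.1, but that section covers only contact after a 911 call. Section 2.10.2.3 uses a 911 response to a hypertensive crisis as an example. Section 2.10.3 sets very high blood pressure apart from ordinary referrals. All three show an intention to act at once; none withholds a procedure or changes the class.

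**Step 3: is the home list consistent within itself?** A heart rate above 120 bpm stops home spirometry, although Table 2 rates it only Check-up. A blood pressure rated Urgent with a 911 offer stops nothing.

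**Step 4: is the clinic limit explained by albuterol alone?** No. Addendum 3, section 12.2, mentions extreme blood pressure in its paragraph on fainting during lung-function testing, and again in a separate paragraph on albuterol. Section 3.2 names the same fainting risk for home spirometry. The albuterol reason is specific to the clinic; the fainting reason is not.

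**Step 5: the boundary in the clinic.** At exactly 180/110, Table 4 calls for emergency care and 6.6.7 withholds the walk. Section 6.9 requires values above 180 or above 110, so it does not withhold spirometry.

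**Step 6: is the measurement available in time?** Section 2.9.4.1 takes heart rate and blood pressure together, three times, and puts heart rate before respiratory testing. Table 1 also lists blood pressure ahead of spirometry. The second and third readings are generally averaged for reporting, so a defined value exists for a stop.

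**The case against.** The strongest reply is that the protocol already treats this reading as an emergency in substance. The 911 offer is the first step of the Emergency class, 2.10.1 calls for immediate handling, and the word Urgent may simply be loose drafting. That is a fair reading of intent. It still leaves the omission of spirometry to inference, because no sentence links it to this row.

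A second reply is that the home exclusions are described as very conservative and rest on two multinational studies of over 14,000 adults without adverse events. Addendum 3, section 6.9, cites the same two studies and still adds a blood-pressure limit.

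Three objections stand in full:

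- The home phase appears complete. Accrual ended in 03/2013 (Protocol Summary), the section 2.16 timeline ends home visits in 2012, and Addendum 3 reports 11,200 completed home examinations. No repeat home visit was found in the plan.
- The agent's prompts (section 2.10.5, Appendix J) and result scripts (Appendix L) are not shown. A reader might infer that participants were in fact tested at dangerous pressures; the documents do not support that, because actual practice cannot be seen.
- A reader might also infer that the clinic rules support withholding the home blood draw. They do not. Addendum 3, section 6.5.5, draws 54.5 or 64.5 mL, against 52.5 mL at home, and sets no blood-pressure limit for it.

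Nor is the Emergency class unusable: acute distress or illness seen at the visit can still trigger it. The gap concerns the blood-pressure reading alone.

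**Conclusion.** The point holds for home spirometry. The exclusions carry no blood-pressure limit, and the Emergency rule is not attached to SBP ≥180 or DBP ≥110, although Table 2 gives that reading an Emergency-type action and Addendum 3 treats it as an emergency. The separate mismatch in Addendum 3 between >180/>110 and ≥180/≥110 is narrow but real.

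The documents do not say how many participants had such readings, and no estimate is made here. With the home phase apparently finished, the practical gain is small. The clinic correction may have more current use: Addendum 6 refers to participants still eligible for clinic examinations at one site. The conclusion rests on the protocol body as shown and assumes that the unseen prompts do not already contain the stop. Nothing here calls for reanalysis of completed visits.

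**What to change.** 1. For any remaining or repeat home visits, add SBP ≥180 mmHg or DBP ≥110 mmHg to the spirometry exclusions in section 2.9.4.2, judged on the mean of the second and third readings described in 2.9.4.1.
2. Label the top blood-pressure row of Table 2 Emergency, so that it matches its own 911 action and Table 4 of Addendum 3. The condition about a chronic finding sits badly with that label. The row cites an outside guideline that is not at hand, so the sponsor should settle the replacement wording.
3. If clinic examinations are still running, change the limit in Addendum 3, section 6.9, to ≥180 or ≥110, in line with sections 6.6.7 and 6.13.

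The cost is one table row, one exclusion line with its prompt, one changed inequality and an IRB amendment; section 2.10.4.1 already routes changes to the referral standards through the IRB. No new measurement is needed. Spirometry would be deferred for those at or above the limit. The Emergency label would also defer the home blood draw when help is declined, which is stricter than the clinic; section 2.10.4.1 lets both be done later. If the sponsor does not want the blood draw deferred, step 1 alone closes the spirometry gap.

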2.9.4.1 Heart Rate and Blood Pressure Measurement

Three blood pressure and heart rate measurements will be collected by trained study staff. Heart rate will always be measured prior to respiratory testing. Blood pressure will be measured three times using standard clinical oscillometric (not mercury-based) equipment and these results will be provided to the participant at the home visit along with information regarding what these blood pressure results mean using a form similar to that being used in the NIEHS Sister Study. Seated heart rate and blood pressure will be taken three times in rapid succession after a 5 minute rest period and the second and third readings will generally be used to calculate average values for analysis and reporting.

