12.2 Potential Risks

The questionnaires and study procedures associated with the clinical exam study present minimal risks to study participants. Adverse events associated with study procedures are expected to be uncommon and limited to mild and transient discomforts. In order to

minimize risks to participants, all study procedures will be conducted by qualified, experienced, and well-trained research staff.

The questionnaires are based on instruments that are widely used in epidemiological studies and administered in the baseline enrollment effort. The main risk in questionnaire administration involves questions about sensitive health topics or personal experiences that may be traumatic. Participants will be told that they can skip any questions that make them feel uncomfortable or end the interview at any time. Questions related to mental health and distress and drug abuse may be more stressful than other questions, but as described above, staff will be appropriately trained and systems have been put in place to deal with any issues that may arise. Participants will also be warned of the possibility of loss of privacy should their de-identified data distributed through controlled access procedures be linked back to them in ways that cannot be foreseen at present.

Pulmonary function testing is considered safe. The primary risk, which is exceedingly rare, is fainting in older participants with impaired lung function. We minimize the chance that this rare event will occur by using very conservative exclusions for pulmonary function testing. To further minimize risk of fainting, pulmonary function testing is done in a seated position, and study staff will be trained to look for signs of dizziness or other problems and to stop the maneuver if necessary. We will also exclude participants from testing who have extremely high blood pressure or rapid pulse rates. The risk of infection is all but eliminated by using disposable mouthpieces (spirettes). These disposable mouthpieces have the additional protection of having a built-in bacterial filter.

The only other health risk is associated with the use of albuterol, a bronchodilator, which may cause some jitteriness and increased heart rate. In order to minimize these risks, participants with abnormal blood pressure or heart rate will not undergo spirometry testing, and all participants will be observed for spirometry-related adverse events prior to discharge from the clinic.

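### Addendum 3 treats 180/110 as an emergency and bars the corridor walk there, but section 6.9 still admits a reading of exactly 180 or 110 to spirometry with albuterol

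*Protocol*

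**What the plan says.** **Clinic exam (Addendum 3).** Table 4 in section 6.13 gives one row to a systolic pressure of 180 or more or a diastolic of 110 or more. The advice there reads "Emergency Care Needed. A hypertensive crisis exists when blood pressure reaches levels of 180 or higher for the systolic (top) number", followed by the matching diastolic figure. Section 6.6.7 uses the same inclusive level for the corridor walk: "The LDCW will not be performed with participants whose systolic blood pressure is greater than or equal to 180", with 110 or more for diastolic. Section 6.9, which covers spirometry before and after four puffs of albuterol, excludes "participants with a blood pressure > 180 mmHg systolic or > 110 mmHg diastolic". Section 12.2 says that "participants with abnormal blood pressure or heart rate will not undergo spirometry testing", and a little earlier describes the excluded group as those with extremely high pressure. It gives no number in either place.

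**Home visit (main protocol).** Table 2 in section 2.10.4.1 labels the same range Urgent and advises "Seek care as soon as possible if confirmed as a chronic condition". Its comment column has the home visit agent offer to contact 911 or help with referral, with an early telephone follow-up. The class definitions above the table describe the first Urgent level as one where "the participant is asked to follow-up with their health care provider in 72 hours", and the second as one or two weeks. Only the Emergency class provides that, if help is declined, the visit goes on "omitting the blood collection and spirometry components at that time". The home spirometry exclusions in section 2.9.4.2 state a heart-rate limit but no blood-pressure limit.

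**The concern.** In one addendum the same reading leads to three actions that do not fit together. At exactly 180 systolic or 110 diastolic, the participant is told to get emergency care and is kept from walking 400 metres, but is not excluded from forced expiratory manoeuvres and a bronchodilator that section 12.2 says may raise the heart rate. Staff who apply 6.9 as written would be following the protocol.

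The home-visit text has a related weakness. It makes the advice to seek care depend on chronicity, and it uses a label that does not bring in the stop on blood collection and spirometry.

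What is at stake is participant safety at a stated threshold. No analysis is involved.

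**Working it through.** The plan gives no figure to reproduce, so the check sets the rules side by side.

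**1. Clinic blood-pressure rules at and around the boundary (Addendum 3).**

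| Rule | Limit | 179 and 109 | Exactly 180 or 110 | 181 or 111 |
|---|---|---|---|---|
| Table 4 advice | ≥ 180 or ≥ 110 | provider within a month | emergency | emergency |
| 6.6.7 corridor walk | ≥ 180 or ≥ 110 | allowed | barred | barred |
| 6.9 spirometry with albuterol | > 180 or > 110 | allowed | **allowed** | barred |

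The rules disagree only in the middle column.

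**2. Can the text show which operator was intended?** Compare the heart-rate limits as well.

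| Source | Blood pressure | Heart rate |
|---|---|---|
| Table 4, outer rows | ≥ 180, ≥ 110 | > 120, < 40 |
| 6.6.7 | ≥ 180, ≥ 110 | ≥ 120, ≤ 40 |
| 6.9 | > 180, > 110 | > 120, < 40 |

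Section 6.9 matches Table 4 on heart rate but not on blood pressure. Section 6.6.7 matches it on blood pressure but not on heart rate. Within each section all four limits follow one convention: inclusive in 6.6.7, strict in 6.9. A slip in 6.9 and a per-test convention are both consistent with this pattern.

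**3. Does 12.2 settle it?** No. It speaks once of extremely high and once of abnormal pressure, without a cut-off. If abnormal were read literally, it could reach Table 4 rows well below 180/110.

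**4. Home visit.**
- *Label.* The row's action (911 offer, care as soon as possible) resembles the Emergency class. The Urgent label points to 72 hours or one to two weeks and omits no procedure. No Table 2 row is labelled Emergency.
- *Condition.* Section 2.9.4.1 says: "Seated heart rate and blood pressure will be taken three times in rapid succession". Such readings cannot establish a chronic condition. Section 8.1.7 gives the same advice for markedly elevated results with no condition attached.
- *Stop.* Section 2.10.1 says a hypertensive crisis found at the visit is dealt with at once and points to 2.10.6.1. That section covers follow-up after a 911 call and states no stop.

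**5. Who can still be affected.**
- *Home visits.* Section 2.3.1 starts recruitment in March 2011 and completes home visits within 26 months: March 2011 + 26 months = May 2013. Addendum 3 reports 11,200 done. None is scheduled after that.
- *Clinic exams.* Exams were still being sought when Addendum 6 was written. It lists 356 (LSU) + 806 (USA) = 1,162 follow-up non-responders as eligible for the exam. This is a pool size, not a count of people with such readings.

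**The case against.** The strongest case against has four parts.

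**The strict limits in 6.9 may be deliberate.** A reader might infer a typing error, because the heart-rate limits there match Table 4 and the blood-pressure limits do not. The documents do not support that inference: 6.9 is strict throughout and 6.6.7 inclusive throughout. This part of the objection stands. It does not remove the mismatch, since a deliberate convention would still leave an emergency reading eligible for testing.

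**Section 12.2 is not a second contradiction.** A reader might take its reference to abnormal pressure as a rule that 6.9 breaks. Read with the nearby reference to extremely high pressure, it is loose wording with no cut-off. This stands too, so the point rests on Table 4 and 6.6.7.

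**Home-visit handling is stronger than the label suggests.** A reader might infer that a hypertensive crisis at home would go unmanaged. The documents say otherwise. Table 2 offers 911 contact, and 2.10.1 calls for immediate handling. Section 2.10.2.3 uses a 911 response to a hypertensive crisis as its example for system alerts, and 2.10.3 singles out extremely elevated pressure as a possible exception to ordinary referral. Labels in Table 2 are loose elsewhere: a heart rate above 120 is a Check-up, yet the advice is to see someone as soon as possible. The computer prompts and result forms are not shown. What survives is narrower: the conditional advice, a label that does not bring in the stop, and no blood-pressure limit for home spirometry.

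**The settings differ.** Only the clinic gives albuterol, and 2.10.4.1 says that levels of urgency can vary across practitioners. This is a fair reason to treat the home-visit point as secondary. It does not explain a difference within Addendum 3 itself.

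**Conclusion.** The point holds as a minor safety correction. Within Addendum 3, a reading of exactly 180 systolic or 110 diastolic is an emergency, bars the corridor walk and leaves spirometry with albuterol permitted. Its origin cannot be told from the text.

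The size is small. Only boundary readings at the clinic are affected. The documents give no frequency for them, and none is assumed. The home-visit wording matters only if such visits are done again under this text. No endpoint, estimate or power figure changes.

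Two assumptions apply. The same reading is taken to feed all three clinic rules; section 6.3 averages the second and third readings for participant reports, while 6.6.7 and 6.9 do not say which value they use. The home-visit part concerns the protocol text alone.

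A reader might also infer that clinic blood collection should stop at this level. Addendum 3 states no such bar, and the omission of blood collection comes only from the home-visit Emergency class.

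**What to change.** **Main change.** In Addendum 3, section 6.9, change the limits to ≥ 180 mmHg systolic or ≥ 110 mmHg diastolic, to agree with Table 4 and 6.6.7. The cost is one line of wording, the matching screening prompt, and a few omitted tests at the boundary.

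**Secondary, if home visits are done again under this text.**
- In Table 2 of section 2.10.4.1, delete the chronicity condition and relabel the row for systolic ≥ 180 or diastolic ≥ 110 as Emergency. The class's omission of blood collection and spirometry then applies when help is declined.
- Add the same limits to the spirometry exclusions in section 2.9.4.2.
- Bring the prompts and result forms into line.

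The cost is wording and a few omitted or deferred tests. Design and sample size are unchanged.
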